The pattern of postoperative opioid consumption will be evaluated at 2 weeks and 6 weeks after the surgery and will be compared between subjects who underwent preoperative opioid education versus those who did not. The hypothesis is that subjects who receive the preoperative opioid education will be less likely to consume opioid tablets after 2 weeks compared to subjects who did not receive the educational intervention.

The rates of prescription refills 12 months after the surgery will be evaluated and compared between subjects who underwent preoperative opioid education versus those who did not. The hypothesis is that subjects who receive preoperative opioid education will be less likely to have opioid refills within the first 12 months postoperatively compared to subjects who did not receive the educational intervention.

The postoperative opioid consumption between subjects with particular clinical conditions (preoperative opioid use, active tobacco use, the presence of a chronic pain syndrome, anxiety, depression) will be compared to subjects without these conditions. The hypothesis is that subjects with these clinical conditions will have higher postoperative opioid consumption rates, including higher rates of opioid prescription refills within 12 months after surgery, compared to subjects without these conditions.

The subjects' opinions about the adequacy of their initial postoperative opioid prescriptions will be compared between subjects who received the preoperative educational intervention versus those who did not. The hypothesis is that subjects who received the preoperative educational intervention will be more likely to answer that their opioid prescription was "more than adequate" or "adequate" compared to subjects who did not receive the educational intervention. The subjects' opinions regarding the adequacy of their initial postoperative opioid prescriptions will be compared between subjects with particular clinical conditions (chronic pain syndromes, anxiety, depression, active tobacco use, and preoperative opioid use) to subjects without these conditions. The hypothesis is that subjects with the clinical conditions will be more likely to answer "less than adequate" regarding their postoperative opioid prescriptions compared to subjects without these clinical conditions.

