4. Describe the primary outcome variable(s), secondary outcome variables, and predictors and/or comparison groups as appropriate for the stated study objectives/specific aims.

Primary outcome variable: mean number of opioid tablets consumed 2 weeks postoperatively

Secondary outcome variables:

1. Patient reported opioid consumption 6 weeks postoperatively
2. Modified surgical pain score (validated questionnaire) at the preoperative assessment and 2 weeks and 6 weeks postoperatively
3. Responses to the Preoperative Opioid Education Study Survey (investigator authored) at the preoperative assessment
4. Responses to the Postoperative Opioid Education Study Survey (investigator authored) at 2 weeks

and 6 weeks postoperatively

5. Evaluate the number of opioid prescription refills postoperatively within the UC Irvine electronic medical record system and California Department of Justice CURES 2.0 database at 2 weeks, 6 weeks, 12 weeks, and 12 months postoperatively
6. Evaluate intraoperative complications (packed red blood cell transfusion, bowel injury, bladder injury, ureteral injury, conversion to laparotomy) – each variable will be measured independently
7. Evaluate postoperative complications (mesh exposure, wound infection, packed red blood cell transfusion, neuropathy, or urinary tract infection within 6 weeks postoperatively or return to the operating room for within 14 days post operatively) – each variable will be measured independently
8. Total daily morphine equivalents prescribed in the hospital prior to discharge – to be calculated using the Opiate Equianalgesic Dosing Chart
9. Post-operative date upon discharge from the hospital
10. Post-operative date that the patient passed a voiding trial and the transurethral catheter was removed
11. Duration of the surgery (in minutes)

Comparison groups: subjects will be randomized to an intervention arm versus control arm. The intervention arm will receive opioid informational pamphlets in addition to the standard preoperative and postoperative instructions and counseling. The control arm will receive the current standard preoperative and postoperative instructions and counseling. The two arms will be stratified by study site (UC Irvine versus Kaiser Permanente Orange County – Irvine).

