Inclusion criteria:

Female

| |
|---|
| 
Age 18-99 years old English speaking Evaluated by a provider within the Urogynecology division at UC Irvine or Kaiser Permanente Orange County – Irvine Medical Center and consented for either a uterosacral ligament suspension, sacrospinous ligament fixation, minimally-invasive colpopexy (either laparoscopic or robotic-assisted laparoscopic), colporrhaphy, or colpocleisis
 
Exclusion criteria: Non English-speaking Cognitive deficits that would prevent the patient from completing the study questionnaires Cancellation of the surgery Combined case with another surgical service (i.e. colorectal surgery)
 |
| 
2. If eligibility is based on age, gender, pregnancy/childbearing potential, social/ethnic group, or language spoken (e.g., English Speakers only), provide a scientific rationale.
 |
| 
The division of urogynecology at UC Irvine exclusively treats female patients with the above stated procedures for the indication of pelvic organ prolapse. As such, male patients would not be eligible to participate since they are not candidates for the above noted procedures due to anatomical differences. The study patient educational pamphlets are only available in English and therefore the study objectives are best observed within an English proficient patient population.
 |

SECTION 4: RECRUITMENT METHODS

| |
|--|
| 
Check any of the following methods that will be used to recruit subjects for this study:
 |
| 
 This study involves no direct contact with subjects (i.e., use of existing records, charts, specimens).
 
Specify database or IRB-approved protocol number (HS#), if applicable:
 |
| 
 Advertisements, flyers, brochures, email, Facebook, and/or other media.
 
Specify where recruitment materials will be posted:
 
If subjects will be recruited by mail, e-mail, or phone, specify how their contact information will be obtained:
 |
| 
 The study will be listed on Clinicaltrials.gov.
 |
| 
 The study will be listed on the UC Irvine Health Clinical Trials web page.
 |
| 
 The UCI Social Sciences Human Subjects Lab/Sona Systems will be used.
 |

| |
|--|

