1. Include an explanation of the study design (e.g., randomized placebo-controlled, cross-over, cross-sectional, longitudinal, etc.) and, if appropriate, describe stratification/ randomization/blinding scheme.

Randomized, non-blinded, controlled trial. Patients will be randomized into intervention (specific patient opioid education performed) and control (standard of care without specific patient opioid education) arms through a randomization scheme in REDCap. Randomization will be stratified by medical center (UC Irvine Medical Center versus Kaiser Permanente Orange County – Irvine Medical Center). Patients and providers will not be blinded due to the nature of the intervention (educational).

2. Provide precise definitions of the study endpoints and criteria for evaluation; if the primary outcomes are derived from several measurements (i.e., composite variables) or if endpoints are based composite variables, then describe precisely how the composite variables are derived.

Primary outcome: mean number of opioid tablets consumed 2 weeks postoperatively

Secondary outcome variables:

1. Patient reported opioid consumption 6 weeks postoperatively
2. Modified surgical pain score (validated questionnaire) at the preoperative assessment and 2 weeks and 6 weeks postoperatively
3. Responses to the Preoperative Opioid Education Study Survey (investigator authored) at the preoperative assessment
4. Responses to the Postoperative Opioid Education Study Survey (investigator authored) at 2 weeks and 6 weeks postoperatively
5. Evaluate the number of opioid prescription refills postoperatively within the UC Irvine electronic medical record system and California Department of Justice CURES 2.0 database at 2 weeks, 6 weeks, 12 weeks, and 12 months postoperatively
6. Evaluate intraoperative complications (packed red blood cell transfusion, bowel injury, bladder injury, ureteral injury, conversion to laparotomy) – each variable will be measured independently
7. Evaluate postoperative complications (mesh exposure, wound infection, packed red blood cell transfusion, neuropathy, or urinary tract infection within 6 weeks postoperatively or return to the operating room for within 14 days post operatively) – each variable will be measured independently
8. Total daily morphine equivalents prescribed in the hospital prior to discharge – to be calculated using the Opiate Equianalgesic Dosing Chart
9. Post-operative date upon discharge from the hospital

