10. Post-operative date that the patient passed a voiding trial and the transurethral catheter was removed
11. Duration of the surgery (in minutes)

C. Research Procedures

1. Provide a detailed chronological description of all research procedures.

The study concept would be introduced to the patients at the consult visit, preoperative visit, on in the preoperative unit prior to surgery. If the patient agrees to participation during any of these encounters, written consent and HIPPA authorization will be obtained and the patient would be randomized to the intervention or control arm using a computerized randomization scheme on REDCap. The randomization will be stratified by the site of the surgery (UC Irvine Medical Center versus Kaiser Permanente Orange County – Irvine Medical Center). If the patient is randomized to the intervention arm, the first opioid informational pamphlet will be provided and reviewed with the patient in addition to standard preoperative instructions. If the patient is randomized to the control arm, standard preoperative instructions will be provided. Patients within both arms of the study will receive standardized postoperative medication prescriptions prior to the surgery. Patients within both arms of the study will complete the modified surgical pain score and preoperative opioid education study survey prior to surgery.

After the surgery is completed, the primary surgeon will decide whether to admit the patient to the hospital and which postoperative analgesics will be administered within the hospital prior to discharge for subjects in both study arms. The patient will follow up for standard postoperative clinic visits at 2 weeks and 6 weeks postoperatively. One to two days prior to the 2 week postoperative visit, the patient will be contacted via telephone to remind her to bring her opioid prescription bottle to the clinic visit.

Between the surgery date and the 2 week postoperative visit, the electronic medical records will be reviewed to evaluate the length of the surgery, intraoperative complications, the postoperative date of discharge, the postoperative date of removal of the transurethral foley catheter, the total daily morphine equivalents that the patient was prescribed prior to discharge from the hospital, and the presence of opioid prescriptions 30 days prior to the surgery. Additionally, the CURES 2.0 Database will be queried to evaluate for opioid prescriptions 30 days prior to the surgery.

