During the 2 week postoperative visit, the remaining opioid tablets will be counted and recorded by a co-investigator. The patient will complete the modified surgical pain score and postoperative opioid education study survey. The UC Irvine electronic medical record system and CURES 2.0 Database will be queried to evaluate for additional opioid prescriptions since the time of surgery. Patients randomized to the intervention arm will receive the second opioid informational pamphlet, which will be reviewed by a co-investigator.

During the 6 week postoperative visit, the patient will complete the modified surgical pain score and postoperative opioid education study survey. The UC Irvine electronic medical record system and CURES 2.0 Database will be queried to evaluate for additional opioid prescriptions since the time of surgery. The patients' electronic medical records will be reviewed after the 6 week postoperative visit to evaluate for postoperative complications.

Twelve weeks after the surgery, the UC Irvine electronic medical record system and CURES 2.0 Database will be queried to evaluate for additional opioid prescriptions since the time of surgery.

If a patient fails to follow up for a postoperative visit, at least two attempts will be made to contact the patient via telephone to collect opioid pill counts and have the patient verbally complete the modified

surgical pain score and postoperative opioid education study survey. Initial statistical analysis will be performed after the 12 week postoperative opioid refill assessment

Twelve months after the surgery, the UC Irvine electronic medical record system and CURES 2.0 Database will be queried to evaluate for additional opioid prescriptions since the time of surgery. Additional statistical analysis will be performed after the 12 month opioid refill prescriptions have been evaluated.

While this is a multi-site trial involving subjects from UC Irvine and Kaiser Permanente Orange County – Irvine, only deidentified data will be uploaded into the REDCap data management system. The lead investigator will maintain a separate key containing patient health information for subjects from both sites, which will be utilized to evaluate for additional opioid prescriptions 12 months after the surgery. Co-investigators from both study sites will not have access to identifiable data from subjects that were not recruited from their particular study site.

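### As the plan reads, opioid tablets already on hand before surgery are never counted, so consumption is understated mainly in preoperative opioid users and the planned user versus non-user comparison can be hidden or reversed

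*Combined protocol and SAP*

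**What the plan says.** - **Outcome.** Section 6.B, item 2, gives one line: "Primary outcome: mean number of opioid tablets consumed 2 weeks postoperatively". Section 1, item 4, repeats it. Neither limits the tablets to a particular prescription.
- **Eligibility.** Section 3.C excludes on language, cognition, cancelled surgery and combined surgical cases. Preoperative opioid use is not an exclusion.
- **Planned comparison.** Section 1, item 3, compares women with and without certain conditions, preoperative opioid use among them, and hypothesises that "subjects with these clinical conditions will have higher postoperative opioid consumption rates".
- **Measurement.** Under Section 6.C, item 1, both arms receive a standardized postoperative prescription before surgery. One to two days before the 2-week visit the patient is telephoned to "remind her to bring her opioid prescription bottle to the clinic visit". At the visit "the remaining opioid tablets will be counted and recorded by a co-investigator".
- **Prior supply.** The same section checks the medical record and the CURES database for the presence of an opioid prescription in the 30 days before surgery. Queries after surgery look for further prescriptions.
- **Analysis.** Section 6.I compares the arms with an unadjusted t-test and makes no allowance for preoperative use.

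**The concern.** The outcome is worded as all opioid tablets consumed, but the measurement described covers one bottle. A woman who already has opioids at home can take those and leave the new bottle partly or wholly full. Her count is then low although her consumption is not. The error falls mainly on preoperative users, the group in which the plan expects high consumption.

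What is at stake first is the user versus non-user comparison in Section 1, item 3, where the error is largely one-sided. The level of the primary outcome in each arm is also understated. The difference between arms is a separate matter and depends on how the education affects the existing supply.

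**Working it through.** **1. The plan's own figure.** Inputs from Section 6.I, item 5: difference 5 tablets, equal to 0.5 SD, so SD = 5 / 0.5 = 10; alpha 0.05; power 80%. With a two-sided normal approximation, n per arm = 2 × (1.960 + 0.842)² / 0.5² = 62.8, rounded up to 63. The stated 63 reproduces, with power 80.1%. The exact t-test needs 64, and 63 gives 79.5%. The sample size is not in question here; the point concerns measurement.

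**2. Can own-supply intake enter the outcome?** Consumption from any supply is the starting count minus the remaining count (plus anything dispensed in between).
- For the postoperative prescription the starting quantity can be known, and the remainder is counted.
- For tablets already at home no starting count is planned, and the call does not ask for those bottles.
- The 30-day check records whether a prescription existed, not how many tablets were left, and it misses leftovers from older prescriptions.
- Queries after surgery show new prescriptions, not use of old tablets.

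So, as written, own-supply intake cannot be calculated.

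**3. Users against non-users (means assumed, not in the documents).** Let users truly take 15 tablets and non-users 10, and let s be the share of the users' tablets that is uncounted. Observed excess = 15 × (1 − s) − 10.

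| s | Observed excess (true value 5) |
|---|---|
| 1/4 | 1.25 |
| 1/3 | 0 |
| 1/2 | −2.5 |

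**4. Level of the outcome (share and intake assumed).** One or two tablets a day for 14 days is m = 14 or 28 uncounted tablets per such woman. With a share p of such women, the mean is low by p × m.

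| p | m = 14 | m = 28 |
|---|---|---|
| 5% | 0.7 | 1.4 |
| 10% | 1.4 | 2.8 |
| 20% | 2.8 | 5.6 |

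The planning control mean is 10. If p and m are the same in both arms, the shortfall cancels and the arm difference does not change.

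**5. Arm difference, conditional case.** Suppose that in these women the education works wholly on uncounted tablets. The observable difference is then 5 × (1 − p). Power at 63 per arm, SD 10, normal approximation:

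| p | Difference | Power |
|---|---|---|
| 5% | 4.75 | 76% |
| 10% | 4.5 | 71% |
| 20% | 4.0 | 61% |
| 30% | 3.5 | 50% |

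**6. Cost of making the all-supply count primary.** If a share p adds m tablets independently of the surgical tablets, SD = √(100 + p(1 − p)m²).
- p = 10%, m = 14: √(100 + 0.09 × 196) = 10.85; power for 5 tablets about 73%.
- p = 10%, m = 28: √(100 + 0.09 × 784) = 13.06; power about 57%.
- p = 20%, m = 28: √(100 + 0.16 × 784) = 15.01; power about 46%.

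If women substitute one supply for the other, the loss is smaller.

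**The case against.** - **The text never says that only the postoperative bottle is counted.** A reader might take that as stated. It is the natural reading of a single bottle requested after a standardized prescription, but the remaining tablets at the visit are not defined. This stands as a limit on the wording. It does not remove the gap, because without a starting count even an extra bottle brought to the visit would not give consumption.
- **A reader might infer that the primary comparison is biased in favour of the education**, because a woman who avoids the new bottle and uses old tablets is scored as a success. The documents do not support that as a finding. Randomization balances women with their own supply on average, and equal uncounted intake leaves the difference unchanged. Bias needs the education to change use of, or switching to, the old supply. The documents give no evidence that it does, and education about opioid risks could equally reduce use of both supplies. For the same reason, the shortfalls in the mean should not be read as erosion of the 5-tablet target difference.
- **The surveys may already ask about opioids at home.** Their items are not in the documents, so this is possible. Nothing links them to the primary outcome.
- **The subgroup hypothesis has a second measure**, refills within 12 months from the records and CURES. This stands, but refills do not show tablets taken from stock.
- **Counting every supply changes the estimand and mixes maintenance use into the outcome.** This stands. Step 6 shows what it could cost in power, and it is a good reason to keep the all-supply count as a supporting analysis.

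**Conclusion.** The point holds as a gap in measurement. If the plan is followed as it reads, opioids taken from a supply held before surgery are missed. Consumption is understated mainly in preoperative users, and the user versus non-user comparison is pushed towards the null or past it. How far cannot be said from the documents. The figures of 15 and 10 tablets, 1 to 2 tablets a day, and prevalences of 5% to 30% are all illustrative. It should not be assumed that every preoperative user takes 14 to 28 uncounted tablets: a prescription in the previous 30 days may be a short course already finished.

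The randomized arm difference is largely protected, and the loss of power in step 5 applies only under the condition stated there. The change is worth making because it is cheap, and because a baseline tablet count not taken before surgery cannot be reliably recovered later.

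**What to change.** 1. State in Section 1, item 4, and Section 6.B that the primary outcome is tablets consumed from the standardized postoperative prescription.
2. Change the reminder call and the 2-week count to cover all opioid bottles, recorded separately by supply. Record opioid tablets on hand at the preoperative assessment, before randomization where possible.
3. Use the all-supply count (on hand plus dispensed, minus remaining) for the comparison of preoperative users with non-users, and as a prespecified sensitivity analysis of the arm comparison.
4. Repeat the primary comparison in women with no opioid prescription in the 30 days before surgery. The plan already collects the data for this.

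The cost is one more line in an existing call, one preoperative question and a slightly longer count. The baseline supply will be partly self-reported, and the all-supply analysis will have a higher variance, so it should support the primary outcome and not replace it. No treatment or prescribing changes.

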**Evaluating the Effect of Preoperative Patient Education
on Postoperative Opioid Consumption, Storage, and
Disposal after Urogynecologic Procedures**

Protocol ID: 2017-11833

Study Protocol and Statistical Analysis Plan
06/04/2018

| | |
|--|---|
| Upload this completed narrative and any supplemental documentation to the IRB Application . | IRB USE ONLY: HS#: 2017-4003 |
| Lead Researcher Name: [name] MD | |
| Study Title: Evaluating the Effect of Preoperative Patient Education on Postoperative Opioid Consumption, Storage, and Disposal after Urogynecologic Procedures | |

CLINICAL TRIAL MASTER PROTOCOL AND INVESTIGATIONAL BROCHURE INFORMATION

| | Master Protocol | Investigator Brochure: | Investigator Brochure: | Sponsor Consent Form Template(s) |
|--|-----------------|------------------------|------------------------|----------------------------------|
| Version #: | | | | |
| Version Date: | | | | |
|  This study is investigator-authored (investigator developed the study and is conducting the study at UCI and/or with other non-UCI sites). | | | | |

NON-TECHNICAL SUMMARY

| |
|--|
| Provide a brief non-technical summary or synopsis of the study that can be understood by IRB members with varied research backgrounds, including non-scientists and non-affiliated members. |
| 
The purpose of this study is to evaluate whether providing patients with specialized preoperative counseling about the risks associated with opioid medications will lead to a reduction of opioid consumption after common urogynecologic surgeries. The study will be a randomized controlled trial that will be performed at two sites (UC Irvine Medical Center and Kaiser Permanente Orange County – Irvine Medical Center). Patients who agree to participate will be randomized to control (standard of care) arm or an intervention (specialized opioid education in the form of patient pamphlets and verbal scripts, which will be performed prior to their surgery and at the 2 week postoperative clinic visit) arm. The randomization will be stratified by medical facility. Assessment of the patients’ opioid consumption will be conducted through physician-mediated pill counts during the patients’ standardized postoperative clinic visits. Any additional opioid prescriptions within 12 months of the surgery will be evaluated by reviewing the patients’ UC Irvine electronic medical records as well as the California
 |

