Department of Justice's Controlled Substance Utilization Review and Evaluation System (CURES) 2.0 database. Additionally, patient pain scores and patients' current storage and disposal patterns of opioid medications will be evaluated through the use of questionnaires during standardized preoperative and postoperative clinic visits.

SECTION 1: PURPOSE AND BACKGROUND OF THE RESEARCH

1. Provide the scientific or scholarly rationale for the research. Describe the relevant background information and the specific gaps in current knowledge that this study intends to address.

Morbidity and mortality from prescription opioid use is a rising epidemic within the United States.¹ The rates of substance abuse admissions and deaths attributable to prescription opioid abuse have significantly increased within the last ten years.²⁻⁴ Unused postoperative opioid medications are a source of opioids that may ultimately be diverted or misused by someone other than the surgical patient. Recent research demonstrated that a significant proportion of patients do not dispose of excess opioid medication and have shared it with another person in the past.⁵ Recent studies have sought to address the optimal postoperative opioid prescription in urologic, obstetrical, and general surgery.⁶⁻⁹ In the literature to date, there is minimal data regarding normative patterns of postoperative oral opioid use amongst patients undergoing urogynecologic procedures. While early research demonstrates that physician education can significantly decrease postoperative opioid prescriptions,¹⁰ there is a lack of data evaluating the effect of patient education on postoperative opioid consumption.

2. Provide relevant preliminary data (animal and/or human).

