Hota et al. evaluated 57 women undergoing urogynecologic surgeries for pelvic organ prolapse and urinary incontinence and reported that the median number of opioid tablets consumed 2 weeks after a minimally invasive urogynecologic surgery was less than 10. Sixty six percent of patients reported having excess opioid tablets at 2 weeks postoperatively and 42% of patients reported that they were going to keep their excess tablets for future use.¹¹ Swenson et al. evaluated 50 patients who underwent minimally invasive urogynecologic surgery for the indication of pelvic organ prolapse and found that the median number of opioid tablets consumed was 13, and that participants only used one third of the amount prescribed.¹² Bates et al. surveyed adult patients who underwent surgery in a urology practice and showed that only 58% of the prescribed pain medication was used and 67% of participants reported having excess medication⁶. Of note, 92% of patients within the study reported receiving no formal disposal instructions for excess opioid medication and of those patients with leftover medication, 91% kept the medication at home. Bartels et al. found that 53% of participants reported taking fewer than five opioid tablets following a cesarean delivery.⁷

3. Describe the purpose, specific aims or objectives. Specify the hypotheses or research questions to be studied.

The purpose of this study would be to evaluate whether a preoperative educational pamphlet addressing the risks and side effects of opioid medications would reduce postoperative opioid consumption after common urogynecologic surgeries for the indication of pelvic organ prolapse. The hypothesis is that patients who receive the preoperative opioid education would consume less opioid tablets after their surgeries.

Additionally, the effect of the preoperative opioid educational intervention on postoperative patient storage patterns and compliance with FDA-recommended disposal patterns of opioid medications

would be evaluated. The hypothesis is that patients who receive the opioid education would have higher rates of safe storage patterns (out of sight, in a locked area) and FDA-recommended disposal patterns (return to a FDA-approved distribution center, mix with an unpalatable substance before disposing in the trash, or flushing down the sink or toilet) compared to patients who did not receive the opioid educational intervention.

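### The primary outcome is tablets consumed, but the plan counts tablets remaining and gives no rule for untaken tablets or refills

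*Combined protocol and SAP*

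**What the plan says.** Section 6.B.2, which asks for precise endpoint definitions, gives one line: "Primary outcome: mean number of opioid tablets consumed 2 weeks postoperatively". The Non-technical Summary says that assessment of "opioid consumption will be conducted through physician-mediated pill counts". Section 6.C.1 describes the procedure: "During the 2 week postoperative visit, the remaining opioid tablets will be counted and recorded by a co-investigator". If the visit is missed, the count is sought by telephone.

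According to Section 6.C.1, both arms receive a standardized prescription before surgery, and its quantity is not stated. The UC Irvine record and the CURES database are searched for further opioid prescriptions at 2 weeks. Section 6.I.3 uses the resulting refills only in a Mann-Whitney comparison, as a secondary outcome. Section 6.I.2 applies a t-test to mean tablets consumed.

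Section 1.3 states that the trial will also evaluate "the effect of the preoperative opioid educational intervention on postoperative patient storage patterns and compliance with FDA-recommended disposal patterns of opioid medications", with more recommended disposal expected in the educated arm. It further hypothesizes that "subjects who receive preoperative opioid education will be less likely to have opioid refills within the first 12 months postoperatively". Section 7.C.1 says that intervention patients will learn about storage and disposal.

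**The concern.** No text links tablets remaining to tablets consumed. The natural link is the standardized quantity minus the count, and that has two faults.

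- **Untaken tablets.** A tablet that left the bottle without being swallowed by the patient is scored as consumed.
- **Refills.** Tablets from a refill are never added to the supply, so the use of a patient with a refill is understated.

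Both faults touch behaviour that the intervention is meant to change. More disposal before the count in the educated arm would raise that arm's apparent consumption. More refills in the control arm would lower that arm's apparent consumption. Each would shrink a true reduction.

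An analyst cannot repair the first fault afterwards. If the number of untaken tablets is not asked for at the visit, it is hard to recover.

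**Working it through.** **Plan's own figure.** Inputs from Section 6.I.5: difference 5, equal to 0.5 SD, so SD = 5/0.5 = 10; alpha 0.05; power 80%. With a two-sided test, n = 2 × (1.960 + 0.842)² × 10² / 5² = 62.8, so 63 per arm, as stated. Power at 63 per arm is 80.1% by the normal approximation and 79.5% by the t-test. The planned means are 10 (control) and 5 (intervention).

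**Model for untaken tablets.** Let N be the tablets prescribed, m the true mean consumed, and p the share of patients who lose all leftovers before the count. Such a patient scores N. Then

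- observed mean = m + p(N − m)
- observed variance = (1 − p) × 100 + p(1 − p)(N − m)²

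**Assumed inputs.** N and p are not in the documents.

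- *N = 30 or 40.* In one cited series (Section 1.2) a median of 13 tablets was a third of the amount prescribed, which implies about 39. Smaller prescriptions are not illustrated. With N = 20 and mean 5, the largest possible SD of a count between 0 and 20 is √(5 × 15) = 8.66, so the planned SD of 10 could not occur. At N = 30 the limit is √(5 × 25) = 11.18.
- *p = 5%.* The nearest figure is a urology survey in which "of those patients with leftover medication, 91% kept the medication at home". There 67% had leftovers, so (1 − 0.91) × 0.67 is about 6% of all patients, at an unstated time. This is not a difference between arms.

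**Case 1: 5% of intervention patients, no controls.**

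- N = 30: intervention mean 5 + 0.05 × 25 = 6.25, difference 10 − 6.25 = 3.75. Intervention variance 95 + 0.0475 × 625 = 124.7, control variance 100, pooled SD 10.60. Power 50%.
- N = 40: intervention mean 5 + 0.05 × 35 = 6.75, difference 3.25. Intervention variance 95 + 0.0475 × 1225 = 153.2, pooled SD 11.25. Power 36%.

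**Case 2: 5% in both arms.**

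- N = 30: control mean 11.0, intervention mean 6.25, difference 4.75. Variances 114.0 and 124.7, pooled SD 10.92. Power 68%.
- N = 40: control mean 11.5, intervention mean 6.75, difference 4.75. Variances 137.8 and 153.2, pooled SD 12.06. Power 59%.

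If instead both arms lose the same mean number of tablets, the difference stays 5.

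**Refills.** If every bottle is counted but set against the first prescription only, the observed difference is 5 − (r_c − r_i) × R, where r_c and r_i are the control and intervention refill rates and R is the refill size. With assumed rates of 10% and 5% and R = 20, it is 5 − 0.05 × 20 = 4.0. Equal rates and sizes leave it at 5. The documents give no 2-week refill rate.

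**Simplification.** Consumption is treated as normal before loss, ignoring the bounds 0 and N.

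**The case against.** The strongest reply is that the plan does not actually state the faulty rule. Dispensed minus remaining is inferred, and the means to correct it may already exist. The Non-technical Summary says that "storage and disposal patterns of opioid medications will be evaluated through the use of questionnaires during standardized preoperative and postoperative clinic visits", and the postoperative survey is completed at the same visit as the count, or by telephone. Its items are not shown. If it records a number of untaken tablets, only the derivation line is missing. This stands, and it makes the claim conditional. But no text connects the survey to the primary outcome.

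Exposure may also be small. The window is 2 weeks, and a call one or two days before the visit reminds the patient to bring her bottle. The second pamphlet is listed after the count. Section 1.3 describes the preoperative material as "a preoperative educational pamphlet addressing the risks and side effects of opioid medications", and nothing says which pamphlet covers disposal. In one cited series 66% of patients still had excess tablets at 2 weeks. The refill hypothesis concerns 12 months, not 2 weeks. All of this stands as a limit on size.

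A reader might go further and infer that the trial risks a false positive because controls give tablets away. The documents do not support that: the plan's disposal hypothesis points the other way, and nothing suggests losses confined to controls. Nor do they support any particular split between arms; the 5% against none above is an assumption.

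**Conclusion.** The gap is real. The endpoint is consumption, the stated measurement is what remains, and the conversion, the treatment of untaken tablets and the role of refills in the primary outcome are all undefined. On the natural reading, the error may differ by arm and would most plausibly mask a true reduction.

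The size is unknown. The illustrative fall in power, to between 36% and 68% from about 80%, rests on a 5% loss rate, loss of all leftovers, and 30 or 40 tablets prescribed. It shows that modest loss could matter, not that it will occur. It would be too strong to conclude that the primary comparison is already biased by a known amount, or that the sample size of 63 per arm is wrong; that figure follows from the plan's inputs. This is a cheap improvement that should be made before data are collected.

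**What to change.** - **Record.** At the 2-week count and in the telephone fallback, in both arms, record how many tablets from postoperative prescriptions were discarded, returned, lost or given away, unless the survey already asks this.
- **Remind.** In the existing call, ask the patient to bring all postoperative opioid bottles, including refills.
- **Define.** Consumed = tablets dispensed (standardized prescription plus postoperative refills found in the 2-week query) − tablets remaining − tablets reported not taken. For a bottle not brought, use the patient's reported remaining count, so that its use is not omitted. Keep opioids prescribed before surgery separate; the planned 30-day preoperative query helps to identify these patients.
- **Report.** Name in advance which version is primary. Give the result both with and without the self-reported subtraction, and show untaken tablets by arm.

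The cost is at most one numeric question, one sentence in a call, a derivation line and one further analysis, all within planned contacts and queries. The sample size does not change. The downside is that the subtraction is self-reported in an unblinded trial. Over-reporting in the intervention arm would favour the intervention, which is why both versions should be reported. Either could reasonably be primary, provided the choice is made beforehand.
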